#### **SUMMARY OF CHANGES**

Ch	Change Section(s) Summary			
CII	ange	Affected	Summary	
1.	Add group of subjects with history of 4-14 moderate to severe migraines/month.	Synopsis, Target Population;, Synopsis, Study Design; Section 1.4.1 Study Design Rationale; Section 4.1 Study Design and Duration; Section 4.3.2 Long Term Treatment Phase; Section 4.3.3 End of Treatment; Section 7.2.2 Selection and Timing of Dose and Administration	Add new group of subjects with a history of 4-14 moderate to severe migraines/month who will dose every other day for 12 weeks. Subjects in this group can take a tablet of rimegepant on non-dosing days to treat a migraine of mild to severe intensity.	
2.	Clarify the number of subjects to be screened and assigned rimegepant.	Synopsis, Number of Subjects; Section 4.3.1 Screening visit / Observation Phase; Section 5, Population	Clarified the targeted number of subjects to be screened and assigned treatment.	
3.	Added study schema for 4-14 moderate to severe migraines/month group	Study Schematic	Added a separate schematic for 12 weeks of treatment for subjects in the 4-14 moderate to severe migraines/month group.	
4.	Clarify Table 1, Schedule of assessments for separate patient groups	Schedule of Assessments	Added a new schedule of assessments for subjects in the 4-14 moderate to severe migraines/month, every other day dosing group.	
5.	Clarify prophylactic migraine medication	Section 5.2 Inclusion Criteria, Inclusion criterion 2f; Section 5.5 Standard of Care and	Clarified that prophylactic migraine medication regimen should not change during the course of the study.	

		Prophylactic Migraine Medication	
6.	Added exclusion criteria	Section 5.3 Exclusion Criteria: Exclusions 1 and m	Added exclusion of BMI $\geq$ 30 kg/m  and exclusion of history of gallstones or cholecystectomy
7.	Modified exclusion criterion	Section 5.3 Exclusion Criteria: Exclusion i	Modified HbA1c to exclude those with HbA1c $\geq$ 6.5%.
8.	Modified prohibited medications	Section 5.4, Prohibited Concomitant Medications	Further clarified that Depakene and valproate are both prohibited medications. Added new prohibited medication of Lamictal (lamotrigine)
9.	Clarified prophylactic and standard of care migraine medications	Section 5.5, Prophylactic and Standard of Care Medications	Clarified that if a patient takes a tablet of study drug and experiences a migraine later that day, after dosing with study drug for the day, the patient should take their standard of care migraine medication as described in this section of the protocol. Patients are not allowed to take more than one tablet of study medication per calendar day.
10.	Clarified discontinuation rule for specific S- STS scores	Section 6.5 Early Discontinuation From the Study	Added criterion for early termination from study due to scores on the Sheehan-Suicidality Tracking Scale per Section 6.2.5
11.	Added definitions for terms mild,	Section 8.1.1, Definitions for Serious Adverse Events	Added definition of terms for mild, moderate and severe adverse events.

moderate and severe		
12. Updated sample size calculations	Section 9.2, Sample Size	Updated sample size of the subpopulation and corresponding sample size calculations.
13. Included references to Table 2	Various	Added references to Table 2, when discussion study procedures, etc.

#### STUDY SUMMARY (SYNOPSIS)

**Title:** A Multicenter, Open Label, Long-Term Safety Study of BHV-3000 in the

Acute Treatment of Migraine

Rationale: Rimegepant is being developed for the treatment of migraine, with a

specific focus on acute treatment. Effectiveness against migraine was demonstrated in a Phase 2b double-blind, randomized, placebo-controlled, dose-ranging study where rimegepant at 75 mg showed efficacy on all four traditional and points; payers abstrabable and phase place [1]

traditional endpoints: pain, nausea, photophobia and phonophobia [1].

This study is being conducted to further characterize the safety and tolerability of rimegepant during longer term treatment of patients with

migraine.

Target Population:

The study will recruit male and female patients, 18 years of age or older with at least a one-year history of migraine (with or without aura) consistent with a diagnosis according to the International Classification of Headache Disorders, 3rd edition, beta version [2]. Patients must have migraine onset prior to age 50, migraine attacks that last 4-72 hours (if not treated) and have had 2-14 migraine attacks of moderate to severe intensity per month within the 3 months prior to the screening visit. A separate group of patients with a history of 4-14 moderate to severe migraines/month during the 3 months prior to the screening visit, will be enrolled and will dose with one tablet of study drug every other day for 12

enrolled and will dose with one tablet of study drug every other day for 12 weeks. After a 30-day observation period of standard of care, up to approximately 2000 eligible patients will be assigned to receive rimegepant. Patients who have participated in BHV3000-301, BHV3000-302 or BHV3000-303 (or another clinical trial with rimegepant) may be considered for participation in this long term safety study if all eligibility criteria are met, however participation in this study is not guaranteed. Enrollment into this study will initially be open to patients with 2-8 moderate to severe migraine attacks per month (primarily the patients from BHV-3000-301 and BHV-3000-302) for approximately three months. After approximately three months, study enrollment will open for patients with a history of 9-14 migraine attacks of moderate to severe intensity per

with a history of 9-14 migraine attacks of moderate to severe intensity per month within the 3 months prior to the screening visit. Lastly, study

enrollment will open for subjects in the every other day dosing group who have a history of 4-14 moderate to severe migraines/month during the 3

months prior to the screening visit.

**Number of Subjects:** 

Approximately 2800 patients will be screened to assign up to approximately 2000 patients to rimegepant.

Of the 2000 patients assigned to rimegepant, up to approximately:

- 1200 will have a history of 2-8 moderate to severe migraine attacks per month,
- 600 will have a history of 9-14 moderate to severe migraine attacks per month, and
- 200 will have a history of 4-14 moderate to severe migraine attacks per month in the every other day dosing group.

#### **Objectives:** Primary Objective: To evaluate the safety and tolerability of rimegepant.

#### **Secondary Objectives:**

- To evaluate the frequency of ALT or AST > 3x ULN with concurrent elevations in bilirubin > 2x ULN in subjects treated with rimegepant.
- To evaluate the frequency and severity of hepatic-related adverse events and the frequency of hepatic-related treatment discontinuations.

#### **Exploratory Objectives:**

- To evaluate the frequency of subjects with elevated liver function tests (AST, ALT or total bilirubin).
- To evaluate the frequency of subjects with ALT or AST elevations
   3x ULN in temporal association with nausea, vomiting, anorexia, abdominal pain or fatigue.
- To explore the contributions of gender, age and exposure to rimegepant to abnormalities in AST, ALT, or bilirubin.
- To investigate the time on treatment and cumulative exposure associated with: (1) hepatic related SAEs and treatment discontinuations; (2) elevations in ALT or AST > 3x ULN with concurrent elevations in bilirubin > 2x ULN.

- To evaluate the number of headache days and severity of migraine attacks while subjects are treated with rimegepant relative to the observational period.
- To evaluate the effect of rimegepant treatment compared to baseline on the 20-Item Migraine-Specific Quality of Life Questionnaire v 2.1 (MSQoL).
- To evaluate the effect of rimegepant treatment compared to baseline on the Migraine Preference of Medication (PoM).
- To examine the scores on the Sheehan Suicidality Tracking Scale.
- To evaluate the effect of rimegepant treatment compared to baseline on the Satisfaction with Medication survey.
- To evaluate the effect of rimegepant treatment compared to baseline on the Migraine Disability Assessment (MIDAS)
- To evaluate the effect of rimegepant treatment compared to baseline on the Clinical Global Impression change (CGI-c) scale.

### Study Design:

This is a multicenter, open-label study to assess the safety and tolerability of long term use of rimegepant, taken up to one tablet per calendar day, in patients with migraine.

The Screening phase includes a screening visit and a 30 day Observation Period. For subjects to be eligible for the study, they must have 2-14 migraine attacks of moderate to severe intensity per month in the 3 months prior to the Screening Visit. Patients enrolled in the every other day dosing group must have had 4-14 migraine attacks of moderate to severe intensity per month during the 3 months prior to the screening visit. Enrollment into this study will initially be open to patients with 2-8 moderate to severe migraine attacks per month (primarily the patients from BHV-3000-301 and BHV-3000-302) for approximately three months. After approximately three months, study enrollment will open for patients with a history of 9-14 migraine attacks of moderate to severe intensity per month within the 3 months prior to the screening visit. Lastly, study enrollment will open for subjects in the every other day dosing group (4-14 moderate to severe migraines/month).

Upon the completion of the screening visit, patients will be provided an electronic diary (eDiary) to document each day of the 30 day Observation Period if a migraine occurred, the migraine intensity and if the migraine was treated. Patients will record the standard of care migraine treatment received on a paper diary. After completing the 30 day Observational Period, the patient will return to the clinic with both diaries for the Baseline Visit. At the Baseline Visit, eligibility for continued participation in the study will be assessed before study medication will be dispensed. After the investigator reviews the results of the baseline laboratory assessments and determines the patient's continued eligibility, the site staff will inform the patient whether or not they are eligible to start dosing in the Long Term Treatment phase. If eligible for the Long Term Treatment Phase, patients will be instructed that they can take study medication at the onset of a migraine (of mild to severe intensity). Patients in the 2-8 or 9-14 moderate to severe migraines/month groups will be instructed that they can take a maximum of one tablet of rimegepant per calendar day during the 52 week Long Term Treatment phase at the onset of a migraine (of mild to severe intensity).

Patients in the every other day dosing group (history of 4-14 moderate to severe migraines/month) will be instructed that they must take one tablet of rimegepant every other calendar day. If patients in this group have a migraine on a day that they are not scheduled to dose with rimegepant, they may take a rimegepant tablet to treat a migraine of mild, moderate or severe intensity. Therefore, patients in this group can take a maximum of one tablet of rimegepant per calendar day for 12 weeks.

Patients are required to record their migraine occurrence and severity and all study medication doses in the eDiary. Patients are also required to continue to record the standard of care migraine treatment taken on a paper diary. Patients will also use the eDiary to complete the Preference of Medication (PoM) questionnaire and the Satisfaction with Medication (SM) questionnaire at specified study timepoints.

At select study visits, patients will complete or will be administered the Migraine-specified Quality-of-Life Questionnaire v 2.1 (MQoLQ), the Migraine Disability Assessment (MIDAS), Clinical Global Impression – change (CGI-c) scale, and the Sheehan Suicidality Tracking Scale (S-STS) on paper forms, at specified study visits.

Additional assessments and visit schedule are outlined in the procedural table in Section 4.3. Procedures include study personnel review of the eDiary and paper diary with the patient, assessment of study medication compliance, monitoring of tolerability and safety (including vital signs, laboratory tests, and electrocardiography). Study visits will be

approximately every two weeks during the first month and then every 4 weeks until Week 52 for subjects in the 2-8 moderate to severe migraine/month group or the 9-14 moderate to severe migraine/month group.

Study visits will be approximately every two weeks during the first month and then every 4 weeks until Week 12 for subjects in the every other day dosing group (those with history of 4-14 moderate to severe migraines/month).

Patients will return to the study site at the end of Week 52 (or Week 12 for subjects in the every other day dosing group (history of 4-14 moderate to severe migraines/month)) (+/- 7 days) for the End of Treatment Visit. There is a Follow-up Visit 14 days (+/- 2 days) after the Week 12/52/EOT Visit.

To closely monitor for potential drug induced liver injury, guidance on reporting potential drug-induced liver injury (DILI) events is provided in the protocol. Lab results that meet predefined LFT abnormality criteria as DILI should be reported as a serious adverse event (SAE). See Section 8.1.5, Potential Drug Induced Liver Injury (DILI).

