Exposure-adjusted on-treatment cumulative LFT elevations will also be summarized for treated subjects with the number and percentage of subjects with LFT elevations, along with patient-years and exposure-adjusted rates based on exposure up to time of first LFT elevation (see Section 4.8.2).

By-subject longitudinal LFT plots will display all normalized results (i.e., LFT ratio of value to ULN) regardless of study period for AST, ALT, ALP and TBL on the y-axis versus study week of laboratory result on the x-axis for treated subjects with any of the following LFT elevations during a safety analysis period (pre-treatment, on-treatment, follow-up): ALT $> 3 \times$ ULN; AST $> 3 \times$ ULN; TBL $> 2 \times$ ULN; ALP $> 2 \times$ ULN. Study week is defined as study day/7 (see Section 5.5). Each figure will also display treated migraine onsets, start of the on-treatment safety analysis period, and start of the follow-up safety analysis period.

Additionally, an evaluation of Drug-Induced Serious Hepatotoxicity (eDISH) scatter plot will display the maximum TBL ratio of value to ULN on the y-axis versus the maximum ALT ratio of value to ULN on the x-axis, where the maxima will be in the same safety analysis period but not necessarily concurrent. Both axes will be on the \log_{10} scale. Ratios $< 0.1 \times$ ULN will be set to 0.1. Sample sizes in the legend will represent subjects with paired ratios. A horizontal reference line will be placed at $2 \times$ ULN, and a vertical reference line will be placed at $3 \times$ ULN. The lower left quadrant will be labeled “Normal Range”, the upper left quadrant will be labeled “Hyperbilirubinemia”, the lower right quadrant will be labeled “Temple’s Corollary”, and the upper right quadrant will be labeled “Possible Hy’s Law Range.” The following eDISH scatter plots will be produced for treated subjects: (1) on-treatment by enrollment group; (2) on-treatment by average rimegepant exposure; (3) on-treatment by average rimegepant exposure for the EOD+PRN dosing group; (4) on-treatment by enrollment group for treated subjects who

took ≥ 14 tablets per 4 weeks for ≥ 12 weeks; (5) by safety analysis period (pre-treatment, on-treatment, follow-up) across enrollment groups pooled; (6) on-treatment by enrollment group for treated subjects who took ≥ 20 tablets per 4 weeks for ≥ 4 weeks; (7) on-treatment by enrollment group for treated subjects with near-daily dosing.

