4.8.2 Adverse Events

Refer to the BHV3000 Core SAP for AE start date imputation, AE counting rules, definition of treatment-emergent adverse events (TEAEs), and definition of AEs related to study drug.

Tables will present the number and percentage of subjects experiencing AEs by SOC and PT, unless specified otherwise.

A by-subject listing of all AEs will be provided for screened subjects that will flag on-treatment and treatment-emergent AEs. Additional by-subject listings of deaths, SAEs, AEs leading to study drug discontinuation, hepatic-related AEs, and AEs of special interest (i.e., potential drug abuse, CV, and suicidality) will be provided for screened subjects. Refer to the BHV3000 Core SAP for listing content and AEs of special interest.

AE Overview

An AE overview without SOC and PT will present the number and percentage of subjects with any the following AEs: any AE; severe AE; AE related to study drug (unlikely related, possibly related, or related); SAE; SAE related to study drug; AE leading to study drug discontinuation; AE leading to death; hepatic-related AE; severe hepatic-related AE; hepatic-related SAE; hepatic-related AE leading to study drug discontinuation; potential drug abuse AE; CV AE; suicidality AE. An AE overview will be produced for each the following analysis periods and populations:

- Pre-treatment AEs for screened subjects by enrollment group and overall
- Pre-treatment AEs for treated subjects by enrollment group and overall
- TEAEs for treated subjects by enrollment group and overall
- On-treatment AEs for treated subjects by enrollment group and overall
- On-treatment AEs for treated subjects by subgroup level and overall for all subgroups of interest specified in Section 4.2.6
- Follow-up AEs for follow-up subjects by enrollment group and overall.

Pre-Treatment AEs

Pre-treatment AEs will be summarized by SOC and PT by enrollment group and overall for screened subjects for the following endpoints:

- AEs
- SAEs.

Pre-treatment AEs will be summarized by SOC and PT for treated subjects by enrollment group and overall for the following endpoints:

- AEs by severity (total, mild, moderate, severe, moderate or severe, not reported)
- SAEs.

On-Treatment AEs

On-treatment AEs will be summarized by SOC and PT for treated subjects by enrollment group and overall for the following endpoints:

- AEs by severity*
- TEAEs by severity

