- TEAEs occurring in $\geq 2\%$ of subjects in any enrollment group after rounding. Percentages will be displayed rounded to integers, and AEs will be displayed in alphabetical order by SOC and PT.
- AEs occurring in $\geq 2\%$ of subjects in any enrollment group or subgroup level[^]
- AEs occurring in $\geq 5\%$ of subjects in any enrollment group by severity (primary safety endpoint, see Section 4.6.1)
- AEs occurring in $\geq 10\%$ of subjects in any enrollment group
- Exposure-adjusted AEs
- AEs related to study drug by severity*
- AEs related to study drug occurring in $\geq 2\%$ of subjects in any enrollment group or subgroup level[^]
- SAEs (primary safety endpoint, see Section 4.6.1)*
- Exposure-adjusted SAEs
- AEs leading to study drug discontinuation (primary safety endpoint, see Section 4.6.1)*
- Hepatic-related AEs by severity (secondary safety endpoint, see Section 4.6.2)[#]
- Hepatic-related SAEs[#]
- Hepatic-related AEs leading to study drug discontinuation (secondary safety endpoint, see Section 4.6.2)[#]
- Additional AEs of special interest: potential drug abuse[^]; CV; suicidality. Potential drug abuse AEs will be displayed in alphabetical order by severity and PT without SOC.

Endpoints marked with “*” will also be summarized by subgroup level and overall for all subgroups of interest specified in Section 4.2.6. Endpoints marked with “#” will also be summarized by subgroup level and overall only for extrinsic exposure factors (see Section 4.2.6). Endpoints marked with “^” will also be summarized by subgroup level and overall only for key extrinsic exposure factors (see Section 4.2.6).

Refer to the BHV3000 Core SAP for exposure-adjusted AEs. Calculations for on-treatment exposure-adjusted AEs will set reference start date to the study drug first dose date, reference end date to the study drug end dose date, and reference last date to the study drug last dose date + 7 days.

Follow-up AEs

Follow-up AEs will be summarized by SOC and PT for follow-up subjects by enrollment group and overall for the following endpoints:

- AEs by severity
- SAEs.

AEs in All Safety Analysis Periods Combined

AEs in all safety analysis periods combined (i.e., pre-treatment, on-treatment, and follow-up) will be summarized by SOC and PT for treated subjects by enrollment group and overall for the following endpoints:

- AEs leading to study drug discontinuation (primary safety endpoint, see Section 4.6.1)

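### The exposure-adjusted AE, SAE and LFT rates set a 12-week group beside groups treated mainly for 52 weeks, and are comparable only if the hazard is constant over time

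*Protocol*

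**What the plan says.** **Treatment length.** The Protocol synopsis (Study Design) says of the every-other-day group: "Therefore, patients in this group can take a maximum of one tablet of rimegepant per calendar day for 12 weeks". Patients in the 2-8 and 9-14 groups "can take a maximum of one tablet of rimegepant per calendar day during the 52 week Long Term Treatment phase". Planned numbers are about 1200 (2-8), 600 (9-14) and 200 (every other day). SAP 2.1 and 4.2.1 add about 20 subjects treated for 12 weeks with a CGRP biologic to the 2-8 column.

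**AE and SAE tables.** SAP 4.8.2: "On-treatment AEs will be summarized by SOC and PT for treated subjects by enrollment group and overall for the following endpoints". Exposure-adjusted AEs and exposure-adjusted SAEs are on that list. For the time base, "Calculations for on-treatment exposure-adjusted AEs will set reference start date to the study drug first dose date", and the end dates are the end dose and the last dose + 7 days. The formula itself is in the Core SAP, which is not among the documents.

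**LFT tables.** SAP 4.6.3.1 plans "patient-years and exposure-adjusted rates based on exposure up to time of first LFT elevation" for cumulative elevations. The default columns of SAP 4.2.1 (enrollment groups side by side, plus overall) apply.

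**Other LFT outputs in SAP 4.6.3.1.** There is a per-subject rate of elevations over non-missing tests. There is also a table of time to first ALT or AST elevation above 3 x ULN in bins from first dose, restricted to subjects who had an elevation.

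**Schedule.** Protocol Tables 1 and 2 draw LFTs at every treatment visit: Weeks 2, 4, 8 and 12 in the every-other-day group, and Weeks 2, 4, 8 and every 4 weeks to 52 in the PRN groups.

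**The concern.** A rate of first events per patient-year is an average of the hazard over the time observed. The EOD+PRN rate averages Weeks 0-12 only. The PRN rate averages Weeks 0-12 with Weeks 12-52. If risk changes with time on drug, the two differ even when risk is identical at every time.

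The every-other-day group was added to evaluate more frequent dosing, so its column will be read against the PRN columns. Crude percentages cannot serve for that reading, because they differ simply through treatment length. For AEs and SAEs, the exposure-adjusted tables are the only planned output by enrollment group that allows for the unequal length, and none is cut to a common window. An apparent excess could be read as an effect of more frequent dosing. An apparent absence of excess could hide a real one.

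**Working it through.** **The plan's own figures.** Neither document states an exposure-adjusted rate, a hazard shape or a dropout rate. The only sample-size figures are the zero-event bounds, and they reproduce: 3/2000 = 0.0015 and 3/800 = 0.00375 (exact: 0.001497 and 0.003738). They are not in dispute.

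**Step 1. Patient-time at full follow-up.** EOD+PRN: 200 x 12/52 = 46 patient-years. PRN: (1200 + 600) x 1 = 1800 patient-years.

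**Step 2. Effect of hazard shape.** Take the same hazard in both groups at every time: r x h to Week 12, then h. The EOD+PRN rate is r x h. For rare events the PRN rate is h(12r + 40)/52, so the ratio is 52r/(12r + 40):

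- r = 0.5: 26/46 = 0.57
- r = 1: 52/52 = 1.00
- r = 2: 104/64 = 1.62
- r = 3: 156/76 = 2.05

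The full first-event calculation (events divided by time to first event) was run with h from 0.02 to 1.0 per patient-year. Values of r and h are assumptions.

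| Early hazard relative to late | Change at Week 4 | Change at Week 12 |
|---|---|---|
| 0.5 | 0.87 | 0.57-0.59 |
| 1 | 1.00 | 1.00 |
| 2 | 1.22-1.24 | 1.48-1.62 |
| 3 | 1.40-1.44 | 1.70-2.05 |

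Example: h = 0.2 and r = 3 to Week 12 gives 60.0 against 30.3 per 100 patient-years, a ratio of 1.98. Assuming 40% yearly dropout in the PRN groups lowers the ratios a little (2.05 becomes 1.92).

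**Step 3. LFT draw density.** EOD+PRN has 4 draws in 12 weeks, or 4/12 x 52 = 17.3 per year. PRN has 14 draws in 52 weeks, or 14.0 per year. The ratio is 17.3/14.0 = 1.24. With an equal probability per draw from 0.1% to 5% (assumed), the first-elevation rate ratio is 1.23-1.24.

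This depends on how long an elevation lasts. The share of onset times that a scheduled draw would catch is:

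| Duration | EOD+PRN | PRN | Ratio |
|---|---|---|---|
| 1 week | 4/12 | 14/52 | 1.24 |
| 2 weeks | 8/12 | 28/52 | 1.24 |
| 3 weeks | 10/12 | 40/52 | 1.08 |
| 4 weeks or more | 12/12 | 52/52 | 1.00 |

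**Step 4. Crude percentages.** At a constant 0.2 per patient-year: 1 - exp(-0.2 x 12/52) = 4.5% (EOD+PRN) against 1 - exp(-0.2) = 18.1% (PRN).

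**Step 5. Common window.** If every group is cut at the same point after Week 12, the scheduled LFT draws are identical (Weeks 2, 4, 8, 12). The ratio at equal risk is then 1.00 for any hazard shape on the clock used.

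**The case against.** The strongest reply is that the plan makes no formal comparison. The study is open-label and non-randomised, the groups were enrolled in sequence with different migraine histories, and the estimands are frequencies. A 12-week cut would not isolate dosing frequency. SAP 4.2.6 already examines intensity through average-exposure and near-daily-dosing subgroups. All of this is correct, and it limits the gain to descriptive reading. It does not make the side-by-side rates comparable.

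For LFTs, two planned outputs help. The per-test rate corrects draw density, though it still pools early and late periods. The time-to-first-elevation table has bins common to all groups, though no at-risk denominator, so it gives no rate. The density effect is also small in counts. At an assumed 0.2%-1% per draw, 200 subjects x 4 draws gives 1.6-8 elevations, against 1.3-6.5 after dividing by 1.24.

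A reader might infer that the tables are biased against every-other-day dosing. The documents do not support this. Neither says that risk is front-loaded; a constant hazard gives no distortion, and a late-accruing one reverses it. The exploratory objectives list time on treatment and cumulative exposure for hepatic events as questions still to be investigated.

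The exact AE denominator is in the unseen Core SAP. If events to last dose + 7 days count while patient-time stops at the end dose (an assumption), a further factor of (13/12)/(53/52) = 1.06 would apply.

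**Conclusion.** The point holds in conditional form. The full-period exposure-adjusted AE, SAE and LFT rates are comparable between the 12-week and 52-week groups only under a constant hazard, which the plan neither states nor justifies. At equal risk the EOD:PRN ratio could lie anywhere from about 0.57 (early hazard half the late one) to 2.05 (three times), with 1.00 for a constant hazard. The direction is unknown. For LFTs, draw density adds up to 1.24 for elevations of 1-2 weeks, 1.08 at 3 weeks and nothing from 4 weeks. AEs and SAEs have the larger gap, since they have no common-window table at all.

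These figures rest on the assumed hazard shapes and on completion of planned treatment. The roughly 20 subjects treated for 12 weeks in the 2-8 column (20/1220 = 1.6%) do not alter them materially.

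**What to change.** In SAP 4.8.2 and 4.6.3.1, add exposure-adjusted AE, SAE and LFT-elevation tables by enrollment group, with events and patient-time cut at the same point in every group. Use these when reading EOD+PRN beside PRN.

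Study day 98, the upper end of the SAP Week 12 analysis window, is a workable cut:

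- Protocol Week 2 is Day 15 and Week 4 is Day 29, so Week 12 is nominally Day 85 and, at +7 days, Day 92. The Week 12 visit is kept.
- The last dose + 7 days window is kept for last doses up to Day 91 (91 + 7 = 98).
- The PRN Week 16 visit (nominally Day 113, earliest Day 106) stays out.

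A cut at exactly 84 days of treatment could drop the Week 12 draw in the every-other-day group. Study days run from enrollment, so PRN subjects who first dose late contribute less time since first dose. The table should state its clock.

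Preferably, also give PRN rates by later interval with patient-time, which would show whether the hazard is constant. Keep the full-period tables, with a footnote that 12-week and 52-week rates are comparable only under a constant hazard and that the groups are non-randomised, so differences are descriptive.

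The cost is SAP wording and a few extra tables from data already collected. PRN data beyond the cut are not used in the common-window tables, but remain in the full-period ones.
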